7.4.1.3. Proportion of Patients Achieving or Maintaining Amenorrhea

7.4.1.3.1. Determination of Amenorrhea

Rules for determining amenorrhea in the randomized treatment period is defined as those who meet one of the following requirements for two consecutive visits (approximately 56 consecutive days). Patients will be deemed to be amenorrheic during a particular visit window according to the following rules (see [Table 11](#)):

- No FP returned due to reported amenorrhea;

OR

- No FP returned due to reported spotting or FP collection with a negligible observed MBL volume coupled with other data indicating infrequent non-cyclic bleeding/spotting as described in [Table 11](#).

If no FP collection because patient failed to collect used products per protocol or due to “Other” reason, the amenorrhea status will be missing. If no FP collection due to retreatment visit or successful retreatment, the amenorrhea status is not applicable.

Missing responses for menstrual bleeding questions in the paper diary will be treated as “No Bleeding” if paper diary compliance rate is $> 70\%$.

Table 11: Rules for Determining Reported Amenorrhea by Visit

Feminine Product Collection ^a	Patient's Paper Diary	Amenorrhea Status
No feminine product collection due to reported amenorrhea	N/A, since paper diary entry is not required per protocol.	Yes
No feminine product collection due to reported spotting or feminine product collection with negligible observed MBL volume defined as <5 mL	
 • Data indicating infrequent, non-cyclic bleeding/spotting defined as bleeding/spotting with feminine product use for no more than 3 consecutive days and no more than 5 days bleeding total per visit window • Diary entry rate > 70% 	Yes

Abbreviations: MBL = menstrual blood loss; N/A = not applicable.

^a There is no requirement for feminine product return rate, as the determination of amenorrhea is based on the Feminine Product Collection eCRF page and the diary response.

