6.2. Treatment Period (Week 52/Baseline to Week 104)

As denoted in the Schedule of Activities (see Table 1-1), certain Week 52 visit procedures in the OLE study will serve as the Week 52/Baseline procedures for patients who are interested in participating in this Randomized Withdrawal study, and these Week 52 procedures will be performed under the informed consent for the OLE study.

Patients will be required to sign an informed consent form for the Randomized Withdrawal study and will be eligible if they meet all the eligibility criteria.

Once eligibility is determined, all additional Week 52/Baseline visit procedures described in the Schedule of Activities (see Table 1-1) that were not performed as part of the Week 52 visit of the OLE study will be completed. These include the following:

- Informed consent;
- Record concomitant medications;
- Dispense study treatment;
- Dispense feminine products;
- Record adverse events, if any.

Patients will record vaginal bleeding and feminine product use in a paper diary each day. Safety monitoring including physical examination, pregnancy tests, and adverse event assessment will

occur at each visit. Additional safety assessments will be performed as described in the Schedule of Activities (see Table 1-1). Bone densitometry will occur at the Week 52/Baseline, and Week 104/Early Termination visits. A transvaginal ultrasound (with or without a transabdominal ultrasound) will be performed at Week 52/Baseline visit.

Study drug compliance will be reviewed at each visit.

Fasting (other than water) for at least 8 hours is required prior to blood sampling on Week 52/Baseline and Week 104/Early Termination visits and for 1 hour after administration of the study drug in the clinic. Laboratory requisitions must indicate whether the patient fasted for the chemistry and lipid testing.

Patients will be randomized 1:1 to blinded treatment with oral relugolix with E2/NETA, once daily, or placebo beginning on the day following the Week 52/Baseline visit and continuing through the Week 104 visit.

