Patients will receive their last dose of study drug in the OLE study on the day of the Week 52/Baseline visit (as per the OLE study protocol), and the patient will be provided blinded study drug to begin dosing the following day. The first dose of study drug will be selfadministered the next morning following the Week 52/Baseline visit. After the Week 52/Baseline visit, a phone call will occur on Week 52 Day 1 (+ 2 days) to document the time of self-administration of the first dose of study drugs and record any reported adverse events. On-treatment study visits will occur every 4 weeks for a total of 104 Weeks. With the initiation of randomized treatment, patients will collect all stained/soiled feminine products and at the study visits return their feminine products for alkaline hematin testing. A venous blood sample (for hemoglobin) must be collected each time feminine products are returned and sent to the central laboratory conducting the alkaline hematin assessment. If the patient is having cyclic bleeding, the site must document the start and stop dates of the patient's menses corresponding to the collected feminine products. The paper diary recording vaginal bleeding and feminine product use should be reviewed at each visit to assess compliance with feminine product collection.

When the alkaline hematin analysis indicates MBL \geq 80 mL, the patient will be asked to return with onset of the next menses, no later than cycle day #7 (where cycle day #1 is the first day of menstrual bleeding), to begin retreatment with open-label relugolix with E2/NETA. The timing of this visit may necessitate an unscheduled visit. The final dose of randomized treatment should be self-administered by the patient the day prior to presenting for retreatment. The first dose of retreatment with open-label relugolix with E2/NETA will be administered at the clinic visit. Feminine products do not need to be collected with the episode of menstrual bleeding associated with the initiation of retreatment, but once the episode is complete, all stained/soiled feminine products must be collected and returned at subsequent visits for alkaline hematin analysis until MBL < 80 mL is observed for two consecutive collections.

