Unscheduled visits may be performed at any time during the study whenever necessary to assess for or follow-up on adverse events, at the patient's request, to initiate retreatment, or as deemed necessary by the investigator. The date and reason for the Unscheduled visit should be recorded in the source documentation. The following activities should be completed at Unscheduled visits: recording of reason for the visit, concomitant medication review, and evaluation of adverse events. In addition, procedures such as vital signs, weight, symptom-directed brief physical examination, central safety laboratory assessment, urine pregnancy testing, pharmacodynamic sampling, 12-lead ECG, study drug compliance, and dispensation, etc., may be conducted as clinically indicated. See the Schedule of Activities (Table 1-1) for tests that may be performed, as indicated by the reason for a visit, at an Unscheduled visit. The investigator should consult with the medical monitor, if needed, to discuss Unscheduled visit testing. The investigator should obtain approval from the sponsor to perform transvaginal ultrasound endometrial biopsy, or DXA, unless urgently indicated.

6.5. **Study Procedures**

6.5.1. **Efficacy-Related Procedures**

6.5.1.1. **Bleeding Diary**

All women enrolled in the study will be provided with a paper bleeding diary along with instructions for its use. Patients will complete the diary daily including compliance with study drug, vaginal bleeding, and use of feminine products.

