Patients were to be asked to collect FPs for alkaline hematin analysis and to return them at each visit until the analysis confirmed the return of heavy menstrual bleeding (defined as menstrual blood loss volume of ≥ 80 mL). The patients were then to be offered re-treatment with open-label relugolix +E2/NETA with the onset of the next menses. They were to continue collection of FPs for alkaline hematin analysis until two consecutive analyses confirmed resolution of heavy menstrual bleeding (menstrual blood loss of < 80 mL). Patients who experienced a return of heavy menstrual bleeding (or terminate early because they have a return of heavy menstrual bleeding) but who decline retreatment with open-label study drug were to complete an Early Termination visit and a 30-day Safety Follow-Up visit.

At the Week 104/Early Termination visit, all other patients were to have an assessment of bone mineral density (BMD) via dual-energy x-ray absorptiometry (DXA). Patients were to complete the bleeding diary daily, including compliance with study drug, vaginal bleeding, and use of FPs.

If a patient enrolls directly into another relugolix clinical study upon completion of the Week 104/Early Termination visit, then the Safety Follow-Up visit and the follow-up procedures performed under this protocol may be waived.

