7.3.2.3. Feminine Product Collection Interval

The FP collection interval at each visit is driven by types of bleeding patterns experienced by the patients, as described below:

- For patients who continue to have cyclic bleeding, the length of the interval depends on the duration of the patient's natural cycle;
- Patients who report irregular, non-cyclic bleeding are instructed to collect and return all FP used between study visits, up to 35 days, as per the schedule of events;
- For patients who report amenorrhea on the Feminine Product Collection eCRF page, an interval of last 35 days of treatment will be reviewed to ensure that reported amenorrhea is not due to incomplete collection.

For patients who are in the midst of an episode of cyclic bleeding at the time of the FP collection visit (or the last visit in the randomized treatment period which is prior to Week 104), the visit window may be extended up to 7 days after Week 104 visit (or last visit) to ensure patients return all used FPs over that bleeding episode.

Per protocol, all used FPs are to be collected at each visit and returned for analysis using the alkaline hematin method. For patients who continue to have menstrual bleeding, study visits are timed such that the FPs used in the entire menstrual bleeding cycle are collected in one container provided at each visit.

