7.3.2.4. Menstrual Blood Loss Volume for Each Feminine Product Collection Interval

Menstrual blood loss volume for each FP collection interval is defined as the MBL volume obtained from the FP returned over the FP collection interval (or the FP collection interval between the two consecutive visits during the randomized treatment period which is prior to Week 104). Sum of MBLs from multiple FP collection kegs (if any) within the same FP collection interval will be used as the total MBL for that visit. The total MBL volume over each FP collection interval will be used to derive the responder status at that visit.

If a patient did not return FP over the FP collection interval prior to retreatment and reported amenorrhea on the Feminine Product Return eCRF page, she will be considered as amenorrheic and her MBL volume will be assigned as 0 mL.

If a patient did not return FP over the FP collection interval prior to retreatment and reported spotting on the Feminine Product Return eCRF page, her MBL volume will be assigned as <5 mL.

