7.3.2.5. Feminine Product Return Rate by Visit

To quantify degree of compliance with FP collection during the randomized treatment period, the FPRR will be calculated based on the inventory of FP returned by day (dates) provided by the vendor, KCAS, the reason why the FP was not collected from the Feminine Product Collection eCFR page, and responses to the paper patient diary questions regarding bleeding experience and the use of FP obtained for the corresponding diary window (see [Table 6](#)). Specifically:

- For those who returned FP at a FP collection visit, the FPRR was calculated as the observed number of days with returned FPs (based on the inventory of FP received by KCAS) divided by the expected number of days with bleeding and use of product as reported on the patient's paper diary within the FP collection interval (as defined above).

$$\text{FPRR} = \frac{\text{observed (No. of days with returned FP [per KCAS])}}{\text{expected (No. of days reported bleeding and use of FP [per Diary])}} \times 100$$

- For those who did not return any FPs:
 - If the reason was "Amenorrheic" or "Patient only had Spotting that did not require the use of Sanitary Products" on the eCRF, their FPRR will be set to 100% because the lack of menstruation obviates the need for FP collection.
 - If the reason was "Patient failed to collect Used Products per Protocol" on the eCRF, their FPRR was set to 0.
 - If the reason was "Retreatment Visit; No Product Collection Required" or "Successful Retreatment; No Product Collection Required" on the eCRF, their FPRR was set to 0.
 - If the reason is "Other", their FPRR was set to 0.

The texts specified for reason "Other" will be reviewed by the medical team to identify those which belong to any pre-defined reasons listed in the first three bullets above and the reason will thus be treated accordingly.

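### SAP Table 11 accepts reported amenorrhea without a diary check on the ground that the protocol requires no diary, but the protocol requires it daily

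*SAP*

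**What the plan says.** SAP 7.4.1.3.1 determines amenorrhea visit by visit in Table 11. For a visit with no products returned because of reported amenorrhea, the diary column reads "N/A, since paper diary entry is not required per protocol" and the status is Yes. The other row, for reported spotting or a collection under 5 mL, does need the diary: no more than 3 consecutive days and no more than 5 days in total of bleeding or spotting with product use in the visit window, and a diary entry rate above 70%. Footnote a to the table says that amenorrhea rests on the collection eCRF page and on the diary.

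The volume and completeness rules sit elsewhere. Under SAP 7.3.2.4, a woman who returned nothing and reported amenorrhea is handled thus: "she will be considered as amenorrheic and her MBL volume will be assigned as 0 mL". Under SAP 7.3.2.5, for women whose reason is amenorrhea or spotting, "their FPRR will be set to 100% because the lack of menstruation obviates the need for FP collection". Table 9 then gives Complete and Responder Yes. For women who report amenorrhea, SAP 7.3.2.3 adds that "an interval of last 35 days of treatment will be reviewed to ensure that reported amenorrhea is not due to incomplete collection".

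On the diary itself, Protocol 6.2 says "Patients will record vaginal bleeding and feminine product use in a paper diary each day", and Protocol 6.5.1.1, after stating that all enrolled women receive a diary, says "Patients will complete the diary daily including compliance with study drug, vaginal bleeding, and use of feminine products". Protocol 6.2 also says "The paper diary recording vaginal bleeding and feminine product use should be reviewed at each visit to assess compliance with feminine product collection". SAP 2.1 restates the duty: "Patients were to complete the bleeding diary daily, including compliance with study drug, vaginal bleeding, and use of FPs".

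**The concern.** The reason Table 11 gives for leaving out the diary is contradicted by the protocol, by SAP 2.1 and by the table's own footnote. As written, a woman whose diary records bleeding with product use, who returns nothing, and whose eCRF reason is amenorrhea counts as amenorrheic at that visit. Spotting, the weaker statement, has to be consistent with the diary; amenorrhea, the stronger one, does not.

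The proportion with amenorrhea at Week 76/EOT is one of three key secondary endpoints in the fixed testing sequence (SAP 7.4.1). It requires the definition to be met at the last two consecutive visits (7.4.1.3.2), so one contradicted report at either visit can decide a woman's result. A daily record that could settle the matter is already collected.

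**Working it through.** The plan gives no figure on this point, so the check sets the rules side by side and then bounds the effect.

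**1. Is the diary required?** Protocol 6.2, Protocol 6.5.1.1, the bleeding-diary row of the Schedule of Activities and SAP 2.1 all say daily. None exempts women with amenorrhea. Table 11's statement is wrong.

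**2. What happens to a contradicted report?** Take a visit with nothing returned and k diary days (k ≥ 1) of bleeding with product use.

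| Basis | MBL | Return rate | Collection | Responder | Amenorrhea |
|---|---|---|---|---|---|
| eCRF reason: failed to collect | Missing | 0% | Incomplete | Missing | Missing |
| eCRF reason: spotting | 4.99 mL | 100% | Complete | Yes | Yes only within Table 11's diary limits |
| eCRF reason: amenorrheic | 0 mL | 100% | Complete | Yes | Yes |
| SAP 7.3.2.5 formula | – | 0/k = 0% | Incomplete | Missing | – |

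The formula is days with returned product divided by diary days of bleeding with product use, times 100. With k = 0 it is 0/0, and setting it to 100% is harmless. With k ≥ 1 the formula gives 0% and the override gives 100%.

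**3. What does the 7.3.2.3 review cover?** The text names no data source and no consequence, and neither Table 9 nor Table 11 refers to it. Its window can be read in two ways:

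- Applied at each visit, 35 days covers a nominal 28-day interval in full.
- Applied once, at the end of treatment, it covers at most 35/56 = 62.5% of the two-visit amenorrhea window (about 56 days), and 35/168 = 20.8% of the 24 × 7 = 168 days to Week 76.

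**4. Amenorrhea rate.** With 360 women randomized 1:1, there are 360/2 = 180 per arm. One woman wrongly counted moves her arm's rate by 1/180 = 0.56 percentage points; nine would move it by 9/180 = 5.0 points. One and nine are assumed counts, shown only for scale. Equal counts in two arms of 180 would leave the difference in rates unchanged.

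**5. Primary endpoint and time to relapse.** Under SAP 7.3.1.2 an event is a measured MBL of at least 80 mL, and a missing visit is not an event. Without consecutive incomplete visits, a woman without relapse is censored at her last available collection. Censoring moves earlier when two or more consecutive visits are incomplete. A contradicted report can therefore keep a woman event-free and under follow-up longer by breaking up such a run. If it falls at her last visit it may also supply the censoring date, because Table 6 footnote b lets the date of an amenorrhea report stand in for a collection date.

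In Sensitivity Analysis 3 (7.3.4.3) it can remove an event. There, one incomplete visit is enough for a woman with no collection after Week 64, and three or more consecutive incomplete visits for the others.

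**The case against.** The best defence is that the diary is not ignored. Sites must review it at each visit for collection compliance, so the eCRF reason should already reflect it. SAP 7.3.2 lists the diary as a source for responder status, 7.3.3 says completeness is checked against it, and 7.3.2.3 promises a review of reported amenorrhea. The different treatment of spotting also has a rationale: spotting days must be counted to qualify as infrequent, while true amenorrhea leaves nothing to count.

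This defeats any claim that nobody looks at the diary. It does not repair the derivation, because no SAP rule says what status follows when the diary contradicts the eCRF reason.

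Four stronger readings are tempting, and the documents do not support them:

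- A reader might infer that the false statement about the protocol underlies the 0 mL, 100% and responder rules too. It appears only in Table 11. The 100% return rate has its own stated reason, that without menstruation there is nothing to collect, and the other rules do not cite the diary statement. Correcting Table 11 alone would leave them unchanged.
- A reader might infer that the 35-day review certainly misses earlier visits. The sentence sits in a list about the interval at each visit, so its scope is ambiguous.
- A reader might infer that nine misclassified women move the primary responder rate by 5 points. They would move from event-free to earlier censoring at most, not to failure. That arithmetic fits only the amenorrhea proportion.
- A reader might infer that a contradicted report can never count as resumed menses. Table 12 row 3, on collection not done per protocol, could be read to include it, although the text of 7.4.2.3.1 is narrower.

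**Conclusion.** Table 11 is wrong as written. Its reason for omitting the diary contradicts the protocol and the SAP, and the rule can count a woman with diary-recorded bleeding as amenorrheic in an alpha-protected endpoint. The missing diary condition in 7.3.2.4, 7.3.2.5 and Table 9 is a separate gap with a different stated reason, and the unspecified review in 7.3.2.3 does not close it.

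The main effect is on the Week 76/EOT amenorrhea rate, at 0.56 points per woman wrongly counted, assuming 180 per arm. For the primary endpoint and time to relapse the effect is confined to censoring dates, and to event status in Sensitivity Analysis 3.

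The documents do not say how often the diary contradicts the eCRF reason. SAP 7.4.2.2 says most patients have amenorrhea at baseline, but half then switch to placebo, so that does not fix how often this row is used afterwards. Sites are blinded, and nothing in the documents indicates a direction by arm. A reader might infer a bias in favour of relugolix; that would be a guess.

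**What to change.** Before unblinding, amend the SAP as follows:

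1. Table 11: delete the statement that the protocol does not require the diary, and apply the table's existing limits (no more than 3 consecutive days and no more than 5 days in total of bleeding with product use per visit window) to the reported-amenorrhea row. If either is exceeded, the visit is not amenorrheic.
2. SAP 7.3.2.5 and Table 9: where nothing is returned for amenorrhea or spotting but the diary for that Table 6 interval shows one or more days of bleeding with product use, use the formula (0%), giving Incomplete and responder Missing. Keep 100% where the diary shows none.
3. SAP 7.3.2.3: state that the review uses the diary and applies to each visit interval.
4. Table 12: let row 3, with its existing threshold (more than 5 days and more than 3 consecutive days), explicitly cover a contradicted amenorrhea report.
5. Where there is no usable diary, keep the eCRF report and tabulate the number by arm.

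Items 1 and 2 use different thresholds deliberately. Table 11's footnote sets no return-rate requirement for amenorrhea, whereas completeness asks whether the products used were measured. A visit with one to three diary days could therefore remain amenorrheic and still be incomplete.

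The cost is SAP wording and minor programming on data already collected. A few visits will change to missing or not amenorrheic.

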7.4.1.3.2. Amenorrhea During the Randomized Treatment Period

Patients achieving or maintaining amenorrhea during the randomized treatment period at Week 76/EOT (or at Week 104/EOT) are defined as those who meet the definition of amenorrhea at last two consecutive post-baseline visits prior to date of last dose of study drug during the randomized treatment period through Week 76 (or through Week 104) visit.

A key secondary endpoint is the proportion of patients who achieved or maintained amenorrhea at Week 76/EOT during the randomized treatment period.

Patients missing amenorrhea reporting for all visits in the study will not be considered as amenorrheic by Week 76 or Week 104.

Proportion of patients achieving or maintaining amenorrhea at Week 76/EOT and at Week 104/EOT will be summarized by treatment and treatment comparisons will be performed using a stratified Cochran-Mantel-Haenszel test.

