9.3. Efficacy Analyses

Unless otherwise specified, efficacy analyses will be conducted using the mITT Population according to the randomized treatment assignment, and stratified analyses will be stratified by the randomization stratification factors. If the group of patients from any of the individual randomization stratification factors comprises less than 10% of the entire mITT population, this stratification factor will be ignored for stratified analyses.

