7. EFFICACY ANALYSES

7.1. General Considerations

Unless otherwise specified, efficacy analyses will be conducted using the mITT population according to the randomized treatment assignment. Stratified analyses will be stratified by the randomization stratification factors, which include pivotal study baseline menstrual blood loss (MBL) volume (< 225 vs. ≥ 225 mL), geographic region (North America vs. Other, where Europe, Latin America, and Rest of World will be pooled together as Other), and duration of relugolix exposure prior to randomization (28 weeks vs. 52 weeks). If the group of patients at any factor level from a randomization stratification factor (eg, patients with pivotal study Baseline MBL volume ≥ 225 mL) comprises $< 10\%$ of the entire mITT population, this stratification factor (eg, pivotal study Baseline MBL volume) will not be used for stratified analyses. In addition, based on the pooled baseline data, there are < 10 patients in 1 of the 8 strata (derived from the 3 stratification factors each with 2 levels, < 5 patients within a randomized treatment group), geographic region will not be used for stratified analysis. Stratification factors of pivotal study Baseline MBL volume (< 225 vs. ≥ 225 mL) and duration of relugolix exposure prior to randomization (28 weeks vs. 52 weeks) will be used in the stratified analysis for more robust strata-adjusted estimation of treatment effect. The stratification category used at the time of randomization (in the Interactive Web Recognition Service [IWRS] system) will be used for all analyses rather than data recorded on the electronic case report form (eCRF) unless otherwise specified. A sensitivity analysis of the primary endpoint will be performed if the data in the IWRS and eCRF for stratification factors differ by $> 5\%$.

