7.4.1. Key Secondary Endpoints

For testing whether relugolix+E2/NETA is statistically significantly superior to placebo for the primary efficacy endpoint as well as the three key secondary endpoints listed below, a fixed sequence testing procedure will be applied to maintain the family wise type I error rate. Under this testing procedure, the primary endpoint will be tested first at a 2-sided 0.05 significance level. If the p value for primary endpoint is < 0.05, the three key endpoints will be tested sequentially in the order depicted in [Figure 1](#).

[figure not shown]
Figure 1: Fixed Sequence Testing Procedure for Primary and Key Secondary Endpoints

Primary Endpoint

- Sustained responder rate at Week 76

Key Secondary Endpoints

- Time to relapse (MBL \geq 80mL)
- Sustained responder rate at Week 104
- Amenorrhea rate at Week 76 / EOT

Abbreviations: EOT = end of treatment; MBL = menstrual blood loss.

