7.4.2. Other Secondary Endpoints

7.4.2.1. Proportion of Patients Who Responded to Retreatment During the Retreatment Period

Proportion of patients who responded (MBL volume of < 80 mL) to retreatment with open-label relugolix 40 mg +E2/NETA during the retreatment period among placebo patients whose MBL volume had returned to \geq 80 mL during the randomized treatment period will be summarized descriptively. The point estimate and its corresponding 95% CIs will be provided.

The change and percent change in MBL volume from retreatment initiation will also be summarized descriptively as a continuous variable every 4 weeks after retreatment initiation during the retreatment period.

7.4.2.2. Change and Percent Change from Week 52/Baseline in Menstrual Blood Loss Volume During the Randomized Treatment Period

The change (for all patients) and percent change (for patients who did not have amenorrhea at baseline) in MBL volume from Week 52/baseline will be summarized descriptively as a continuous variable at each visit during the randomized treatment period including Week 76 and Week 104 visits. Observed MBL volume for each timepoint will be used to calculate change and percent change from Week 52/Baseline. In addition, the change and percent change in MBL volume from Week 52/baseline will also be summarized descriptively as a continuous variable at each visit during the cumulative treatment period.

For change and percent change in MBL volume, mixed-effects model will not be used to derive LS means (and 95% CIs) due to skewed distribution of MBL volumes (majority of patients experiencing amenorrhea with MBL volume set as 0 mL at baseline). Descriptive statistics (medians and simple means) will be provided for each treatment group.

Categorical summary of change in MBL volume will be provided by grouping patients into three categories: who had increase, no change, and decrease in MBL volume from Week 52/Baseline over time by visit for cumulative treatment period. A figure will also be provided to display the percentages for each category by treatment group every 12 weeks from Week 52/Baseline up to Week 104.

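### The confirmatory amenorrhea test is valid, but its strata leave out amenorrhea status at Week 52/Baseline, and adjusting for it could narrow the interval at little cost

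*SAP*

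**What the plan says.** SAP 7.4.1.3.2 sets the endpoint: "A key secondary endpoint is the proportion of patients who achieved or maintained amenorrhea at Week 76/EOT during the randomized treatment period". SAP 7.4.1 states that "a fixed sequence testing procedure will be applied to maintain the family wise type I error rate", and amenorrhea at Week 76/EOT stands last in that sequence. The comparison method is given in one line, "treatment comparisons will be performed using a stratified Cochran-Mantel-Haenszel test", and the section names no strata.

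The strata follow from SAP 7.1. Pivotal baseline MBL volume (below 225 mL, or 225 mL and above) and prior relugolix exposure (28 or 52 weeks) "will be used in the stratified analysis for more robust strata-adjusted estimation of treatment effect". Geographic region is dropped because "there are < 10 patients in 1 of the 8 strata". The default in Protocol 9.3 is that "stratified analyses will be stratified by the randomization stratification factors", unless otherwise specified.

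Baseline amenorrhea appears elsewhere in the SAP:
- 7.3.2.2 fixes Week 52/Baseline MBL before the first randomized dose.
- 7.4.2.2 gives as its reason for not modelling MBL the "majority of patients experiencing amenorrhea with MBL volume set as 0 mL at baseline".
- 7.4.2.3 uses a baseline MBL of 0 mL to define the menses-resumption population.

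**The concern.** The endpoint counts women who achieve amenorrhea together with women who maintain it. Women already amenorrheic at Week 52/Baseline can only maintain it, and the others must achieve it. The two groups may well have different chances of success. Randomization was not stratified on this status and the test does not adjust for it, so a chance imbalance between arms passes into the estimated difference. That is not bias, because the standard error allows for it, but it is avoidable noise if the status is prognostic.

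The SAP adjusts for baseline values elsewhere. Its mixed models include the baseline value as a covariate (7.1.2), and the bone mineral density ANCOVA includes baseline density as well as age, race and BMI (9.3.3.1). At stake is the width of the interval for a confirmatory endpoint and, if the true effect is modest, some power.

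**Working it through.** **The plan's own figure.** SAP 2.2 gives at least 90% power for the primary endpoint: 360 patients, 1:1, 60% against 40%, two-sided 0.05, 20% dropout. Evaluable patients per arm: 180 × 0.8 = 144. With a pooled null variance:

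- null term: 1.96 × √(2 × 0.5 × 0.5 / 144) = 0.1155
- alternative SE: √((0.24 + 0.24) / 144) = 0.0577
- power: Φ((0.20 − 0.1155) / 0.0577) = Φ(1.46), or 92.8%

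With 180 per arm it is 96.9%. The figure reproduces, but it concerns the primary endpoint. The documents state no power or rates for amenorrhea, so every rate below is an assumption.

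**Large-sample formula.** Let q be the share amenorrheic at baseline. Let a₁, a₀ be the active-arm success rates and b₁, b₀ the placebo rates, in women with and without baseline amenorrhea. Let ā and b̄ be the overall arm rates. With n per arm, n times the variance of the risk difference is:

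- unadjusted: U = ā(1−ā) + b̄(1−b̄)
- adjusted: W + H, where W = q[a₁(1−a₁) + b₁(1−b₁)] + (1−q)[a₀(1−a₀) + b₀(1−b₀)] and H = q(1−q)[(a₁−b₁) − (a₀−b₀)]² / 2

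Example: q = 0.70, active 80%/20%, placebo 30%/5%.

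- ā = 0.62 and b̄ = 0.225, so U = 0.2356 + 0.1744 = 0.4100
- W = 0.7 × (0.16 + 0.21) + 0.3 × (0.16 + 0.0475) = 0.3213
- H = 0.21 × 0.35² / 2 = 0.0129
- reduction: 1 − 0.3341 / 0.4100 = 18.5%

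**Simulation.** Mantel-Haenszel risk differences were compared using the four planned strata and using eight (four × baseline amenorrhea), with N = 360. The planned strata had assumed shares of 40/25/20/15% and were taken as unrelated to outcome. Variance reduction at q = 55%, 70% and 85%:

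| Assumed rates (amenorrheic/not at baseline) | Formula | Simulation |
|---|---|---|
| Strong in both arms: active 80/20, placebo 30/5 | 22.3, 18.5, 11.5% | about 23, 18, 9% |
| Strong in active only: 80/20, 10/10 | 13.1, 11.6, 7.8% | about 10, 10, 4% |
| Weak: 65/45, 12/8 | 2.1, 1.8, 1.1% | 0 to 1% |
| Not prognostic: 60/60, 10/10 | 0% | about −1% |

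Simulated reductions are mostly somewhat below the formula, which ignores the cost of extra small strata (about 1%, last row). Simulation noise accounts for part of the remaining gap. In the first row at q = 55%, the SE falls from 0.0475 to 0.0416.

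**Power and error.** In all these scenarios the treatment effect is at least 34 points, and power is 100% with four or eight strata. With smaller effects, a strong predictor, N = 288, and q = 55%, 70%, 85%:

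- 20 points (60% against 40%): 92.2 to 96.2%, 92.4 to 96.0%, 92.0 to 93.7%
- 10 to 13 points: 45.4 to 52.5%, 53.9 to 59.8%, 62.6 to 66.5%

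Simulated type I error was 4.6% to 5.5% across both versions.

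**Cell sizes.** The smallest planned stratum under the assumed shares holds 0.15 × 360 = 54 women. Those not amenorrheic at baseline would number about 24, 16 and 8 at q = 55%, 70% and 85%, both arms together.

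**The case against.** The planned test is sound and follows the protocol's default. The SAP had just moved from eight strata to four for the sake of robust estimation, and this proposal returns to eight, spreading a non-amenorrheic minority over four of them. That stands as a cost, though a limited one. A CMH statistic sums over strata and does not fail when one is thin, unlike the log-log statistic for the primary endpoint in SAP 7.3.1.1. The protocol's rule also leaves room for a specified exception.

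Three stronger readings are tempting, and the documents do not support them:

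- *Baseline amenorrhea is the strongest available predictor.* No section ranks predictors or gives rates by baseline status. Placebo patients stop the drug under which they were amenorrheic, so the status may predict little in that arm.
- *The planned strata bring no benefit.* They respect the randomization and keep the layout simple.
- *Pooling hides whether amenorrheic women stay amenorrheic.* SAP 7.4.2.3 and 7.4.2.4 analyse menses resumption among women amenorrheic at baseline, with a treatment difference and interval. SAP 7.4.2.2 adds shift tables by baseline MBL category. What is missing is narrower: the two-visit Week 76/EOT endpoint itself, by baseline status.

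It is also fair to object that baseline amenorrhea is not ready for use as a stratum. SAP 7.4.2.3 takes it as 0 mL, whereas the endpoint (7.4.1.3.1, Table 11) needs two consecutive visits and admits spotting or less than 5 mL with diary support. A woman who only spots at baseline could be counted as achieving amenorrhea with no change in bleeding. This stands and has to be settled in the fix.

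**Conclusion.** The point holds as a matter of efficiency. The test controls type I error as planned, and nothing in it is wrong. It passes over a baseline variable that is fixed before dosing and that the SAP already uses elsewhere. The likely trade is favourable: a variance reduction of about 4% to 23% if baseline status is strongly prognostic in at least one arm, 0% to 1% if it is weak, and a loss of about 1% if it is not prognostic. If the treatment effect is large, the benefit is a tighter interval and not more power. At assumed effects of 10 to 20 points with a strong predictor, the scenarios above gain about 2 to 7 percentage points of power.

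These sizes rest on assumed amenorrhea rates, assumed baseline prevalence of 55% to 85% (the SAP says only that it is a majority), and planned strata unrelated to outcome. If pivotal MBL or prior exposure already carries part of the same information, the added gain would be smaller.

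**What to change.** Before unblinding, amend SAP 7.4.1.3.2 to:

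1. List the CMH strata by name and add Week 52/Baseline amenorrhea (yes/no). Naming them also avoids doubt about region, which SAP 7.1 drops but 7.3.1 still lists for the primary test.
2. Define baseline amenorrhea in advance, either as MBL of 0 mL as in 7.4.2.3 or aligned with Table 11, with a rule for missing baseline MBL.
3. Report a Mantel-Haenszel risk difference with 95% CI at Week 76/EOT and Week 104/EOT, or a covariate-adjusted one if cells prove sparse. SAP 7.4 promises intervals for differences, but no stratum-adjusted method is named for this endpoint.
4. Tabulate the endpoint by baseline status, to complement the menses-resumption analysis.

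No new data are needed. The cost is a short amendment and some programming, up to eight strata with few non-amenorrheic women in some, and a stated departure from stratifying by randomization factors only. If the sponsor prefers to keep the planned test, the adjusted risk difference should at least be prespecified as supportive.
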